# **Background: The Impact of Chronic Pain**

Chronic pain is pain that lasts longer than 3 months and affects 18% of the Scottish population (NHS QIS, 2008). Unlike acute pain, it is not an indication of sinister disease processes. In the process of learning to live with chronic pain, people may have experiences of being disbelieved by family, friends and health professionals, struggle with beliefs of being a burden on their loved ones and feel disappointment at not being able to fulfil previously held roles in the family (Smith & Osborn, 2007). Chronic pain becomes a stigma and these experiences, in conjunction with debilitating physical symptoms, can have a profound impact on mood, behaviour and general wellbeing. It is not the intensity of the pain that affects quality of life; the issue is more relational, for example, the negative beliefs that someone may hold about their pain (Lamé et al., 2005). Negative cognitions and emotions are activated by pain-related difficulties and multi-disciplinary treatments for chronic pain target the management of these internal experiences and daily functioning, rather than attempting to eliminate the physical sensation of pain.

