## **Principal Research Question**

 Do self-compassion and psychological flexibility mediate change in a Compassion-Focused Therapy group for adults with chronic pain?

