# Design

This study will follow a within-group (non-randomised) effectiveness-implementation design (Curran, 2012). Five self-report measures will be completed by participants at three specified time periods (pre-, mid- and post-group; see *Procedure* below).

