## **Analysis**

The analysis will focus on the proposed mediating factors (self-compassion and psychological flexibility) and how they explain the outcome of the CFT-incorporated group intervention. In order to study the processes of change, this study will measure change in mediators and outcomes over the course of the group.

In a mediation model, the effect of the independent variable (IV; CFT group) on a dependent variable (DV; outcome/change in symptoms) is conveyed through a third mediating variable. In order to be a mediator, a variable must change during the intervention, be associated with the intervention, and have an impact on the outcome.

In this study, it is hypothesised that self-compassion and/or psychological flexibility are the mediating variables that explain the influence of the group intervention on eventual outcome, i.e. the overall change in symptoms at the end of the group. Linear regression and nonparametric bias-corrected bootstrap, which corrects for skew in the data, will be applied to the data using SPSS, using the PROCESS macro. An effect of mediation will be indicated if the confidence interval does not contain zero.

Missing data will be handled using either the maximum likelihood or multiple imputation method, as recommended in literature.

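### The mediation rule combines a bias-corrected interval with an either-mediator claim and sets no level, primary outcome or multiplicity rule; if the mediators move but are unrelated to outcome, about 11–17% of studies would falsely claim mediation on one outcome

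*Combined protocol and SAP*

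**What the plan says.** The decision rule is one sentence under Analysis: "An effect of mediation will be indicated if the confidence interval does not contain zero". The interval comes from linear regression with a "nonparametric bias-corrected bootstrap, which corrects for skew in the data", run in the PROCESS macro. No confidence level or number of resamples is given.

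- **Mediators.** Under Analysis, "it is hypothesised that self-compassion and/or psychological flexibility are the mediating variables", so either may count. The Principal Research Question asks "Do self-compassion and psychological flexibility mediate change in a Compassion-Focused Therapy group for adults with chronic pain", which joins the two. The Psychological Flexibility section describes flexibility, inflexibility and twelve dimensions, but does not say which MPFI score is the mediator.
- **Outcome.** Analysis speaks of "the overall change in symptoms at the end of the group" without defining it. The measures sections supply five outcome scores: HADS anxiety, HADS depression, SWEMWBS, BPI interference and BPI severity. None is named as primary.
- **Conditions.** Analysis also says that, to be a mediator, "a variable must change during the intervention, be associated with the intervention, and have an impact on the outcome". It does not say whether these are tested or only define the concept.
- **Design.** "This study will follow a within-group (non-randomised) effectiveness-implementation design".
- **Size.** Sample Size asks for 53–71 participants for .8 power, read from a cited guideline.

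Some pages between Analysis and References were not available, so the omissions are established only for the text supplied.

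**The concern.** A programme can raise self-compassion and flexibility without either being related to symptom change. A mediation analysis has to be able to rule that case out, and two features of the stated rule work against it. First, the bias-corrected interval rejects more often than its nominal level when one path is present and the other is zero, at about this sample size. Second, *and/or* gives two chances of success with no adjustment. Leaving the outcome undefined could add further chances.

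The reason given for the method is also wrong. Bias correction adjusts the limits for median bias in the bootstrap distribution of the indirect effect; it does not correct skewness in the data.

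Behind this lies a specification gap. The independent variable is the CFT group, which every participant attends. It does not vary, so the regression that produces the interval is not defined by the text.

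**Working it through.** **1. The plan's own figure.** Sample Size quotes r = 0.33–0.55 for the first path and 0.47–0.66 (absolute) for the second. These were taken as standardised paths with an independent variable that varies between people, and bias-corrected 95% intervals were simulated:

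- 0.33 and 0.47: power about .72 at n = 53 and .845 at n = 71; .80 is reached at about n = 64.
- 0.44 and 0.57: about n = 38 is enough.
- 0.55 and 0.66: about n = 25 is enough.

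So 53–71 is of the right order for the weakest correlations. Its end points cannot be reproduced, because the guideline table is not in the documents.

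**2. Model assumed for false claims.** Because the group variable is constant, the single-arm indirect effect is taken as

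indirect effect = (mean mediator change) × (slope of outcome change on mediator change).

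The slope is set to zero, so any interval that excludes zero is a false claim. Mediator change is in SDs of the change score. Level 95% (assumed), n = 53 and 71, 1000 resamples, mostly 1000–2400 simulated studies per setting.

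**3. The interval.** With z0 = Φ⁻¹(share of bootstrap values below the estimate), the bias-corrected limits are the bootstrap quantiles at Φ(2·z0 ± 1.96). When the mediator clearly moves, this shift tends to push the limits away from zero.

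**4. Per interval.** At 0.5 SD the bias-corrected interval is falsely positive in about 8–9% of studies and the percentile interval in about 5–6%. Over 0.33–0.8 SD, and with a between-person variable at r = 0.33–0.55, the bias-corrected range is about 6.3–9.1%.

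**5. Either of two mediators, one outcome.** For independent tests, P(at least one) = 1 − (1 − p)²:

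- p = .05: 1 − .95² = .0975.
- p = .085: 1 − .915² = .163.

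Allowing for correlated mediators, simulation gives about 11–17%. Separate and joint mediator models give similar results.

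**6. How the two-mediator figure moves with the assumptions.**

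| Reading or setting | At least one false claim, one outcome |
|---|---|
| Mediators change 0.33 SD or more | 11–17% |
| Change 0.2 SD | 7–9% |
| No change | 1–2% |
| The three conditions run as extra p < .05 tests | 8–10% |
| Both mediators required | 1–4% |

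**7. Ceiling if the outcome stays open.** Five scores × two mediators = 10 pairs. Independent tests at exactly 5% give 1 − .95¹⁰ = .401. The bias-corrected simulation gives 48–60% with uncorrelated residuals, 37–49% at correlation .5 and 29–38% at .7: about 30–60% overall. If the mediators do not move, it is 5–6%. The documents give no correlations among the outcome scales.

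**8. Effect of the remedy.** Percentile intervals with Holm over two mediators (first step .05/2 = .025, a 97.5% interval) bring the one-outcome rate to about 5–7%. Holm with the bias-corrected interval kept leaves 8–11%.

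**9. What the remedy does not reach.** If mediator and outcome changes correlate for non-causal reasons at an assumed r = .2 or .3, a 97.5% percentile interval still excludes zero in 22–32% or 46–62% of studies.

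**The case against.** **The principal question joins the mediators.** A reader might infer a false answer to that question in about one study in six. The documents do not support this. The question says *and*, and if both mediators must succeed on one named outcome the rate is 1–4%. The higher figure belongs to the *and/or* hypothesis under Analysis. This objection stands, and the wording has to be reconciled.

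**The risk is conditional.** It needs mediators that move and have no relation to outcome. The documents give no expected mediator change. This also stands, so the condition must accompany the figure. The case is not remote, since the plan itself expects mediators to change.

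**Ten pairs is not the plan.** A reader might take 30–60% as the study's error rate. Analysis speaks of one overall change in symptoms, SWEMWBS measures wellbeing rather than symptoms, and Background says that treatment manages internal experiences and functioning "rather than attempting to eliminate the physical sensation of pain". The figure is a ceiling only.

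**The interval may not decide alone.** The three conditions, if tested, lower the rate to 8–10%. The text does not attach them to the decision rule, so this is unresolved.

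**The simulated model is an assumption.** This is true, because the plan's regression is undefined. A version with a between-person variable gave similar rates, so the direction does not depend on the single-arm form.

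**The method change is small.** Moving from 8–9% to 5–6% per interval is a refinement, and it does nothing about confounded change in an uncontrolled study. That limits what the remedy can claim, but does not justify keeping the less accurate interval.

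**Conclusion.** The point holds in conditional form and should be acted on. As written, a bias-corrected interval with either mediator counting exceeds a nominal 5% when the mediators move by about 0.33 SD or more without relation to outcome: about 11–17% for one outcome and two mediators. This rests on an assumed 95% level, n = 53–71 and an assumed single-arm model. The missing level, primary outcome and MPFI score would on their own be missing detail. What makes this an analysis problem is that the stated method and the either-mediator rule inflate error when followed.

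A reader might also infer that the sample is too small. That is not shown: the documents give no mean mediator change, and power under the revised rule ranges from adequate to low depending on it. What follows is that the .8 needs restating. Confidence is moderate, because the fitted model is not specified.

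**What to change.** 1. State the confidence level, use percentile bootstrap intervals, and delete the clause about correcting skew in the data.
2. Name one primary outcome and one MPFI score; label the rest secondary or exploratory.
3. Reconcile *and* (Principal Research Question) with *and/or* (Analysis). If either mediator may count, apply Holm over the two. If both must, require both at the full level with no Holm step.
4. Write out the within-group regression, and say whether the three conditions are tested or the interval alone decides.
5. State that, without a control group, a positive result shows that mediator and outcome change together, not that one causes the other.
6. Restate the .8 power for the final rule and model.

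No new data are needed. The cost is power. From the planned rule (bias-corrected, taken as 95%) to Holm's first step (percentile 97.5%):

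| Setting | n = 53 | n = 71 |
|---|---|---|
| Between-person model, r = .33 and .47 (weakest quoted) | .73 to .53 | .84 to .69 |
| Single-arm, r = .47, change 0.33 SD | .70 to .51 | .82 to .69 |
| Single-arm, r = .47, change 0.5 SD | .94 to .84 | .98 to .94 |

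In the single-arm model the full Holm procedure recovers about .01–.02. At the weakest quoted correlations the stated .8 would not hold under the revised rule.

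### The plan requires a mediator to change, but its decision rule does not test for change unless path a is defined as the mediator's mean change, which the plan does not do

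*Combined protocol and SAP*

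**What the plan says.** The Principal Research Question asks: "Do self-compassion and psychological flexibility mediate change in a Compassion-Focused Therapy group for adults with chronic pain". The Design section describes a "within-group (non-randomised) effectiveness-implementation design", so there is no control group.

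The Analysis section names the CFT group as the independent variable. The dependent variable is the outcome or change in symptoms, described further on as "the overall change in symptoms at the end of the group". To count as a mediator, the section says, "a variable must change during the intervention, be associated with the intervention, and have an impact on the outcome". On method: "Linear regression and nonparametric bias-corrected bootstrap, which corrects for skew in the data, will be applied to the data using SPSS", run through the PROCESS macro. The decision rule follows: "An effect of mediation will be indicated if the confidence interval does not contain zero".

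The section also says that change in mediators and outcomes will be measured. It gives no test, estimate or threshold for mean change in self-compassion, psychological flexibility or any outcome. It does not say which quantity the interval is for, at what level, or what PROCESS will take as the predictor when everyone receives the same intervention. No other available section supplies these.

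**The concern.** The plan sets three conditions for mediation and then decides on one interval. Whether that interval covers the first condition, that the mediator changed, depends on what it is an interval for. A regression of individual change on individual change describes how people's changes vary together. It says nothing about whether the average moved: people whose self-compassion rose may improve and people whose self-compassion fell may worsen, with a group mean of zero.

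At stake is the answer to the principal question. An analyst who follows the rule to the letter could report that self-compassion mediated change in the group when self-compassion did not rise on average. By the plan's own definition, that variable is not a mediator.

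**Working it through.** **1. Inputs.** From the Sample Size section: n = 53 to 71, and correlations of 0.33 to 0.55 for flexibility processes and 0.47 to 0.66 in size for acceptance with outcomes. The sample size is read from a published guideline that the document does not reproduce, so it is used here only as n. Alpha is not stated; two-sided .05 and a 95% interval are assumed.

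**2. The independent variable is constant.** With x = CFT group for everyone, Σ(xᵢ − x̄)² = 0, so the slope of the mediator on x is 0/0. PROCESS needs some other predictor, and the plan does not name one.

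**3. Slopes ignore mean change.** Let mᵢ be participant i's mediator change and yᵢ the outcome change:

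b = Σ(mᵢ − m̄)(yᵢ − ȳ) / Σ(mᵢ − m̄)²

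Replace every mᵢ by mᵢ + k. The mean becomes m̄ + k, each deviation mᵢ − m̄ is unchanged, and so is b. The same holds for the slope of m on any person-level x, for the partial slope with x in the model, and within every bootstrap resample. The interval is therefore identical for any k, positive, zero or negative. This is algebra and needs no distributional assumption.

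**4. Illustration.** Assume zero mean mediator change and a correlation r between mediator change and outcome change. By the Fisher approximation, the chance of a significant slope is Φ(atanh(r)·√(n − 3) − 1.96).

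- r = .33, n = 53: 0.3428 × 7.071 − 1.96 = 0.464, giving 68%.
- r = .33, n = 71: 0.3428 × 8.246 − 1.96 = 0.867, giving 81%.

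Under bivariate normality the sample mean and the sample slope are independent. Requiring significant mean improvement as well therefore multiplies each figure by 0.025: 0.68 × 0.025 = 1.7% and 0.81 × 0.025 = 2.0%. Simulation agrees. Range over r:

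| r | n = 53 | n = 71 |
|---|---|---|
| .20 (assumed) | 30% | 39% |
| .33 | 68% | 81% |
| .47 | 95% | 99% |
| .55 | over 99% | over 99% |

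**5. Three-variable version with a bias-corrected bootstrap.** This used 1,000 simulated studies with 600 draws each and no mean change in mediator or outcome. It assumed a mediator-outcome correlation of −.58. Where baseline scores serve as X, it also assumed test-retest reliability of .80 (mediator) and .94 (outcome). The share of studies declaring mediation depends on X:

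| X | n = 53 | n = 71 |
|---|---|---|
| Pre-group outcome | 20% | 23% |
| Pre-group mediator | 44% | 55% |
| Early change, r = .33 with mediator change | 74% | 85% |
| Early change, r = .55 with mediator change | 98% | 99.7% |
| Time, paired (path a = mean change) | 7.7% | 6.2% |
| Time, stacked rows ignoring pairing | 0% | 0% |

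Adding a two-sided paired test of mediator change brings the first four rows down to between 0.8% and 4.6%.

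**6. Cost of the added condition.** The chance that a true mean improvement passes comes from the noncentral t distribution with n − 1 degrees of freedom and noncentrality d√n, where d is the standardised mean change. At d = 0.3 the noncentrality is 2.18 (n = 53) and 2.53 (n = 71), giving 57% and 70%. At d = 0.4 the chance is 82% and 91%; at d = 0.5 it is 95% and 99%.

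**The case against.** The strongest reply is that the plan describes a mediation model in PROCESS, so the interval is naturally the one for the indirect effect a × b. Path a is the intervention's effect on the mediator. If the within-group intervention is coded as time, path a is the mean change and the rule does test it; the rate under no mean change is then about 6 to 8% in the paired version. A reader might infer that the rule can never detect an absence of change. The documents do not support that reading, because they leave X undefined. Equally, they do not say that time is X, and time as X fits poorly with an outcome defined as one overall change per person. The gap is therefore conditional, and it is tied to the undefined predictor. Choosing a different person-level predictor would not close it (working, step 3).

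A reader might also take 68 to 81% as the plan's false-positive rate. It is not. It is ordinary power for a two-variable slope at an assumed correlation, with no X, no indirect effect and no bootstrap. The Sample Size section gives no change-on-change correlation: its .33 to .55 are offered as evidence that the group relates to flexibility, and .47 is an acceptance-outcome figure.

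Finally, one might want the outcome to change significantly on average too. Whether mediation requires a total effect is debated, and the plan's list of conditions does not ask for a mean change in the outcome. That should not become a condition here.

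**Conclusion.** The point holds in conditional form. The plan calls change in the mediator necessary, states no check of it, and gives a rule that carries no information on mean change in any regression with one row per participant. The exception is a model in which path a is the mean change, which the plan does not specify.

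The invariance is exact. The percentages are illustrations. Under zero mean mediator change, r = .33 and two-sided .05, a significant slope appears in about 68% (n = 53) to 81% (n = 71) of studies, against about 2% once mean improvement is also required. Bootstrap versions range from 20% to nearly 100% depending on X, and that spread is not a property of the plan.

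A reader might go further and infer that the programme moves nothing, or that a significant interval would be meaningless. Neither follows. No change here means no average change. A slope between individual changes is a real association; it does not by itself meet the plan's definition of mediation. The wording should be settled before the data are analysed.

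**What to change.** In the Analysis section, replace the sentence giving the decision rule with text that does the following:

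- Define path a as the mediator's mean within-person change over a prespecified window: week 1 to week 5 if the mediator is to precede the final outcome. Report week 1 to week 11 as well, since the condition as written covers the whole intervention.
- Define path b as the slope of outcome change on mediator change.
- Declare mediation for a mediator only if the 95% interval for path a excludes zero in the direction of improvement and the 95% bootstrap interval for path b (or for a × b, with the choice named in advance) excludes zero.
- Otherwise, report the result as an association between individual changes.
- Report each outcome's mean change with its 95% interval, without making it a condition.

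This takes a few sentences and one paired comparison per measure. Both mediators are already collected at weeks 1, 5 and 11.

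The cost is power when true mediator change is small: the added condition is passed in 57 to 70% of studies at a standardised change of 0.3 and in 95 to 99% at 0.5. For 80% power the change must be about 2.80/√n, that is 0.39 (n = 53) or 0.33 (n = 71). The rule also leaves one limit in place: with no comparator, a mean change cannot be attributed to the programme, and the report should say so.
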